## APPENDIX 2: ERT WITHDRAWAL SCHEDULE OF EVENTS

PROCEDURE*	ERT Withdrawal Visit (a)	ERT Withdrawal Monitoring Visits Week, +/- 2 days (b)										ERT Withdrawal Follow- Up Visit (within 12 weeks of ERT withdrawal) (c)
		1	2	3	4	6	8	10	12			
Concomitant Medications	X	X	X	X	X	X	X	X	X			X
Physical Examination	X											X
Vital Signs (d)	X											X
AE Assessment	X	X	X	X	X	X	X	X	X			X
ERT Administration Log	X	X	X	X	X	X	X	X	X			X
Clinical Laboratory Tests	X											X
Liver Panel (e)	X	X	X	X	X	X	X	X	X			X
GAG Testing in Urine	X	X	X	X	X	X	X	X	X			X
IDUA / GAG Testing in Blood	X	X (g)	X	X (g)	X	X	X	X	X			X
PFTs (f)	X											X
6MWT (f)	X											X
ERT Clinical Assessment												X

\* Assessments associated with ERT withdrawal that are duplicated at regular scheduled study visits should be waived if visits are combined (see [Appendix 1](#)).

- a) ERT Withdrawal visit may occur at or at any time after the Week 12 visit (refer to [Section 11.4](#) for additional guidance).
- b) Weekly ERT Withdrawal Monitoring visits will take place on a weekly basis for the first 4 weeks, and on a biweekly basis for the last 8 weeks following the ERT Withdrawal visit until the ERT Withdrawal Follow-Up visit. ERT Withdrawal Monitoring visits have assessments that do not require evaluation at the clinical site, and may therefore be conducted at home if the subject is remote. Blood and urine samples at these visits may be collected by a qualified home health nurse. Assessments for AEs and concomitant medications may be conducted by study staff over the phone.
- c) The ERT Withdrawal Follow-Up visit can occur at any time up to 12 weeks after ERT withdrawal at the discretion of the Principal Investigator. ERT does not need to be restarted at the end of the ERT Withdrawal Follow-Up visit.
- d) Vital signs (weight, systolic/diastolic blood pressure, heart rate, respiratory rate, and temperature; refer to the Study Reference Manual).
- e) Liver panel does not need to be drawn as a separate sample if clinical laboratory tests are obtained at the same visit.
- f) As permitted by subject's capacity.
- g) May be waived for pediatric subjects (cohorts 4 through 7) at the discretion of the Principal Investigator to minimize required blood volumes.

## APPENDIX 3: IMMUNOSUPPRESSION REGIMEN

Weight of Subject (kg)	Oral Prednisone (mg/day)					
	Day -2 to Day 0	Week 1	Week 2	Week 3-16	Week 17-19	Week 20
≥ 60	60	60	30	15	5	STOP
55	60	60	30	15	5	STOP
50	50	50	25	15	5	STOP
45	45	45	25	15	5	STOP
40	40	40	20	10	5	STOP
35	35	35	20	10	5	STOP
30	30	30	15	10	5	STOP
<30	1 mg/kg	1 mg/kg	0.5 mg/kg	0.25 mg/kg	0.25 mg/kg every other day	STOP

Prednisone or equivalent corticosteroid regimen is commenced 2 days prior to Day 0 of SB-318 infusion and given once daily unless otherwise stated. Subject's liver function will be monitored twice a week while on prednisone or equivalent corticosteroid. Blood for liver panel shall be drawn 2 to 4 days apart when possible, except for the first week when it will be drawn on the Day 1 and Day 7 visits. Tapering of prednisone or equivalent corticosteroid will only proceed if ALT/AST activity levels are stable or declining (based on the 2 assessments of the preceding week).

If subjects develop increased ALT > 2 fold Baseline while on prednisone or equivalent corticosteroid or after stopping prednisone or equivalent corticosteroid, the prednisone or equivalent corticosteroid regimen may be adjusted or restarted at the Principal Investigator's discretion after consultation with the Medical Monitor.

Twice a week liver panel testing should continue until the prednisone or equivalent corticosteroid course has been terminated.

An ACTH stimulation (cosyntropin) test will be performed prior to the first prednisone or equivalent corticosteroid dose and again during Week 20 or at the end of the scheduled taper to ensure that the adrenal cortical function has not been suppressed. Should prednisone or equivalent corticosteroid treatment be repeated due to increased transaminase activity, the ACTH stimulation test will be repeated at the end of taper at the Principal Investigator's discretion.

#### **APPENDIX 4: INSTRUCTION FOR LIVER BIOPSY SAMPLE COLLECTION AND TISSUE PREPARATION**

SB-318 uses ZFN-gene specific targeted insertion of a hIDUA donor transgene into the liver albumin genome locus in subjects with MPS II to provide long-term production of hIDUA. To determine the efficiency of SB-318, liver tissue will be obtained by liver biopsy for analysis by histopathologic examination, testing for GAG levels, and site specific molecular analysis at the albumin locus. AFP levels will be monitored throughout the study, and abnormal results will be investigated by clinical evaluation and MRI. Any subject who has an elevated AFP and/or an MRI mass suspicious for HCC or greater than 2 cm will undergo liver biopsy. Histopathologic examination and integration site analysis will be performed to determine the origin and nature of the tumor.

##### **Liver Biopsy Sample Collection and Tissue Preparation**

Liver biopsy will be obtained at selected visits unless contraindicated by a Principal Investigator or physician. The liver biopsy should be divided into 3 samples when possible. One liver biopsy sample will be collected in 10% neutral buffered formalin and processed for histopathological evaluation. Two liver biopsy samples will be flash frozen in liquid nitrogen. Samples may be stored in a -80 °C freezer before shipment. The weight of liver tissue obtained from each biopsy sample will be forwarded to Sangamo.

The efficiency of SB-318 in targeting insertion of hIDUA donor transgene to the liver will be measured by site specific molecular analysis of integration events at the albumin locus.

Additionally, the frequency of other genomic modification events like small insertions and deletions (indels) will be determined by Next Generation Sequencing (NGS) at the albumin locus and at the SMCHD1 locus, the only known off-target site of SB-318.

In addition, for any subject who undergoes liver biopsy due to an elevated AFP and/or an MRI mass suspicious for HCC, the albumin locus will be sequenced by NGS to examine the genetic diversity at the albumin ZFN cleavage site, which may provide information about the clonal origin of the suspicious mass. A single or limited number of modified albumin genotypes or AAV integration sites would indicate that the cells were derived from the clonal expansion of modified hepatocytes. A similar sequencing analysis will also be performed on the SMCHD1 locus to evaluate the genetic diversity at the only known off-target site of SB-318.

Mucopolysaccharidosis type I (MPS I) is a lysosomal storage disease caused by deficiency of α -L-iduronidase (IDUA). IDUA is an enzyme that is required for the degradation of the glycosaminoglycans (GAGs) dermatan sulfate (DS) and heparan sulfate (HS). The enzyme deficiency is the result of mutations in the gene encoding IDUA. The inability to degrade GAGs leads to their accumulation within lysosomes throughout the body, with consequent multiorgan dysfunction and damage. The clinical severity of MPS I depends on the nature of the mutational changes and the degree of residual IDUA enzyme activity.

According to the National Institute of Neurological Disorders and Stroke factsheet for MPS I, the estimated incidence is 1 in about 100,000 newborns for severe MPS I, 1 in about 500,000 newborns for attenuated MPS I, and 1 in about 115,000 newborns for individuals whose disease symptoms fall between severe and attenuated. It has been estimated that 50-80% of all MPS I patients present with the severe form of the disease (Muenzer et al. 2009).

Current therapies for MPS I include hematopoietic stem cell transplantation (HSCT) and enzyme replacement therapy (ERT). HSCT can prevent or reverse most clinical features and is recommended for those with the severe form of the disease (Hurler syndrome [MPS IH]). However, the reported mortality rate after HSCT is 15%, and the survival rate with successful engraftment is 56%, although recent improvements in HSCT procedure have improved overall outcomes (Boelens et al. 2013). Patients with the attenuated forms of the disease (Hurler-Scheie syndrome [MPS IHS], Scheie syndrome [MPS IS]) are treated with ERT using laronidase (recombinant human IDUA; Aldurazyme). The limitations of ERT include the need for life-long treatment; development of neutralizing antibodies; inability to cross the blood brain barrier; continued cardiac, orthopedic, and ocular complications; and the inconvenience of weekly intravenous (IV) infusions.

In this study, the objective and rationale for the proposed SB-318 investigational therapy is to abrogate or decrease the need for ERT using *in vivo* genome editing. The proposed treatment employs recombinant adeno-associated virus (rAAV) comprising engineered zinc finger nucleases (ZFNs) to site-specifically integrate a corrective copy of the human iduronidase enzyme (hIDUA) transgene into the genome of subjects' own hepatocytes *in vivo*. Integration of the hIDUA transgene is targeted to intron 1 of the albumin locus, resulting in stable, high level, liver-specific expression and secretion of hIDUA into the blood. Placement of the hIDUA transgene under the control of the highly expressed endogenous albumin locus is expected to provide permanent, liver-specific expression of hIDUA for the lifetime of an MPS I patient.

The purpose of the Statistical Analysis Plan (SAP) is to describe the analyses and data presentations for Sangamo's protocol SB-318-1502 (Amendment version 7). This SAP outlines the types of analyses that will address the study objectives and explains in detail how the data will be handled and analyzed. It contains the definitions of analysis sets and statistical methods for the analysis of endpoints. Since this is an exploratory Phase I study, all analyses will be descriptive and exploratory in nature. No hypotheses testing will be carried out.

2. Objectives

2.1. Primary Objective

The primary objective of this study is to evaluate the safety and tolerability of SB-318.

2.2. Secondary Objectives

The secondary objectives of this study are to evaluate:

- The change from baseline over time in the following assessments:
 - IDUA activity in blood
 - GAG testing in urine
 - Frequency of ERT administration.
- To evaluate AAV clearance

2.3. Exploratory Objectives

The exploratory objectives of this study are to:

- Evaluate the change from baseline over time in the following assessments:
 - GAG levels in tissues (including blood, liver tissue, and cerebrospinal fluid[CSF])
 - Gene modification at the albumin locus in the liver.
 - Imaging, functional, and neurocognitive testing related to MPS I.
 - Immune response to AAV2/6, ZFNs, and IDUA.

3. Investigational Plan

3.1. Overall Study Design and Plan

This is a Phase 1/2, multicenter, open-label, single-dose, dose-ranging study with sequentially enrolled age cohorts: age ≥ 18 (adult cohorts 1 through 3), age 12 to 17 (pediatric cohorts 4 and 5), and age 5 to 11 (pediatric cohorts 6 and 7). The duration of study participation will be approximately 39 months for each subject, including approximately 3 months for screening followed by 36 months for treatment and study follow-up.

Up to 27 subjects may be enrolled in this study

Subjects who satisfy all inclusion/exclusion criteria will be enrolled into one of the following treatment cohorts:

Cohort	ZFN 1 (SB- 47171) (vg/kg)	ZFN 2 (SB- 47898) (vg/kg)	hIDUA Donor (SB- IDUA) (vg/kg)	Total rAAV (vg/kg)
1	1.00E+12	1.00E+12	8.00E+12	1.00E+13
2	5.00E+12	5.00E+12	4.00E+13	5.00E+13
3	1.20E+13	1.20E+13	9.60E+13	1.20E+14
4	TBD	TBD	TBD	TBD
5	TBD	TBD	TBD	TBD
6	TBD	TBD	TBD	TBD
7	TBD	TBD	TBD	TBD

Subjects who received ERT prior to study enrollment will continue to receive ERT during the study and remain on their current schedule per standard of care unless they undergo protocol-specified ERT withdrawal per protocol. However, ERT will be omitted during the week of the SB-318 infusion to facilitate accurate baseline testing (e.g., of GAG levels in urine, blood, and of IDUA activity in blood) and to allow a week free of ERT after the SB-318 infusion.

Cohort #	Age Range (y)	Total Dose (vg/kg)	# Subjects
1	≥18	1.00E+13	1
2	≥18	5.00E+13	2
3	≥18	1.20E+14	2
4	12-17	TBD	2
5	12-17	TBD	2
6	5-11	TBD	2
7	5-11	TBD	2

For each dose cohort after Cohort 1, two subjects will be dosed at least 4 weeks apart. SMC review will occur after all subjects in each cohort have ≥ 4 weeks of safety data.

The pediatric cohorts will be enrolled only after review of cumulative adult safety data by the SMC. The starting dose for pediatric cohorts 4 through 7 will be decided based on SMC review of study data and must meet pre-defined safety criteria.

After being discharged from the hospital or acute care facility, study visits are scheduled on Day 7; Weeks 2, 4, 6, 8, 12, 16, 20, 24, 28, 32, 36, 40, 44, 48, and 52; and Months 15, 18, 21, 24, 27, 30, 33, and 36. Liver function tests (aspartate aminotransferase [AST], alanine aminotransferase [ALT], total and direct bilirubin, alkaline phosphatase (ALP), lactate dehydrogenase (LDH), albumin, and total protein levels) will be conducted for evaluation of AAV mediated immunogenicity twice a week during the first 20 weeks after SB-318 infusion, and then subsequently at all study visits.

3.2. Study Endpoints

3.2.1. Primary Endpoints

The primary endpoint of this study is the incidence of treatment-emergent AE's (including SAEs).

Additional safety evaluation will be included:

- Routine hematology, chemistry and liver function laboratory tests, vital signs, physical exam, ECG, ECHO, and concomitant medications.
- Monitoring of chimerism in post-HSCT subjects.
- Cranial nerve exam and muscle strength testing.
- Serial alpha-fetoprotein (AFP) testing and magnetic resonance imaging (MRI) of liver to evaluate for liver mass.

3.2.2. Secondary Endpoints

The following are secondary endpoints of this study:

1. Change from baseline over time in the following assessments:
 - IDUA activity measured in blood.
 - Total GAG, DS GAG, and HS GAG (expressed as a ratio to creatinine) measured in urine.
 - Monthly and annualized frequency and dose of Aldurazyme (or equivalent ERT).
2. AAV2/6 clearance measured by vector genomes in plasma, saliva, urine, stool, and semen by polymerase chain reaction (PCR).

3.2.3. Exploratory Endpoints

The following are exploratory endpoints for this study:

- Change from baseline over time in the following assessments:
 - Total GAG, DS GAG, and HS GAG measured in tissues (including blood, liver tissue, and CSF).
 - Percentage and durability of gene modification at the albumin locus in liver tissue obtained at biopsy.

- Forced vital capacity (FVC) measured by pulmonary function tests (PFTs).
- Distance walked measured by six-minute walk test (6MWT).
- Joint range motion (JROM).
- MRI of liver to evaluate liver and spleen volume.
- MRI of brain and cervical spine to evaluate clinical soft tissue and/or bone.
- Neurocognitive abilities by WASI-II, WPPSI-IV, or BSID-III, and by VABS-II.
- Eye exam for corneal clouding and vision testing.
- Histopathological exam of liver tissue
- Immune response to AAV2/6, ZFNs, and IDUA measured in serum

Immune response to ZFNs and IDUA have not been performed.

3.3. Treatments

SB-318 is a combination of 3 recombinant adeno-associated virus serotype 2/6 (rAAV2/6) vectors that encode:

- ZFN 1 (SB-47171): Left-side ZFN that targets base pairs 447-461 of the albumin locus relative to the transcription initiation site, labeled as SB-A6P-ZLEFT
- ZFN 2 (SB-47898): Right-side ZFN that targets base pair 468-485 of the albumin locus relative to the transcription initiation site, labeled as SB-A6P-ZRIGHT
- hIDUA Donor (SB-IDUA): DNA repair template that encodes a promotorless hIDUA transgene, labeled as SB-A6P-HRL

The prepared investigational product will be administered via IV infusions while the subject is in hospital or an acute care facility. Subjects will remain in the hospital or acute care facility for at least 24 hours after completion of SB-318 infusion for observation and will be discharged when all AEs and vital signs (temperature, heart rate, respiratory rate, and blood pressure) are stable.

3.4. Dose Modifications

No dose modifications are possible within an individual subject since this is a single infusion study.

4. General Statistical Considerations

Study days will be numbered relative to the date of SB-318 infusion. For assessments on or after the date of SB-318 infusion, the study day of events from SB-318 infusion is calculated as the date of event minus the date of infusion. For assessments prior to the date of SB-318 infusion, the study day of events from SB-318 infusion is calculated as the date of event minus the date of infusion. Thus, the study day of event before the date of the infusion will be negative number, and the study day of the date of infusion will be 0.

Baseline is defined as the last non-missing measurement prior to the SB-318 infusion. Where only date is available, the date of the collection must be prior to the date of SB-318 infusion. Where time is also available, the time of the collection must be prior to the time

of SB-318 infusion. For example, for vital signs parameters, measures that are taken at the latest time prior to the infusion will be defined as baseline values. Measurements that are obtained after infusion will be considered as post-baseline values. If the measurement of a variable is not made on a given subject prior to infusion, then that subject will be considered not to have a baseline value for that variable. Change from baseline is defined as post-baseline assessment minus baseline assessment.

Continuous data will be summarized using the following descriptive statistics: number of subjects (n), mean, standard deviation (SD), median, minimum and maximum, where appropriate. Categorical data will be summarized using the frequency count (n) and percentage (%) of subjects for each category, where appropriate.

Unless specified otherwise, all the summary tables will be presented by treatment cohort and overall, and all the collected data will be presented in the listings, and data displayed in the listings will be sorted by treatment cohort and subject identifier.

No imputation will be applied for missing data unless otherwise specified.

All analyses will be conducted using SAS® Version 9.3 or later. The Medical Dictionary for Regulatory Activities (MedDRA 23.0) will be used for coding adverse events.

Concomitant medication data will be coded using the World Health Organization (WHO) Drug Dictionary.

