### **6.1 Screening**

The objective of Screening is to identify subjects who meet the stated inclusion and exclusion criteria and who are willing and able to participate in the study. Screening may take up to approximately 3 months and may be performed across several visits.

The following assessments and procedures will be performed:

- Obtain a signed and dated subject informed consent form and authorization document to use and disclose medical information prior to performing any study-specific procedures.
- Obtain a complete medical history.
- Review and record concomitant medications.
- Review the inclusion and exclusion criteria.
- Collect demographic information.
- Assign a subject number.
- Physical examination.
- Vital signs.
- Assessment of AEs.
- ERT administration log.
- 12-lead electrocardiogram (ECG).
- Echocardiogram (ECHO).
- Chest x-ray.
- Pregnancy test (for females of childbearing potential only).
- Clinical laboratory tests.
- Liver panel.
- MPS I gene sequencing.
- SNP analysis.
- Viral load.
- Neutralizing antibodies to AAV2/6.

- GAG testing in urine (collect samples on 3 separate days, each collection occurring at least 7 days after the previous, and all collections occurring at least 7 days after ERT administration [+/-1 day] but prior to the next ERT infusion).
- IDUA / GAG testing in blood (collect 7 days after ERT administration [+/-1 day]).
- Circulating AFP level.
- Pulmonary function tests (PFTs).
- VABS-II (Vineland Adaptive Behavior Scales) test.
- Neurocognitive abilities assessment.
- MRI of liver.

Subjects may be re-screened for participation in the study in the judgement of the Principal Investigator and after consultation with Sangamo. For re-screening, the following assessments performed in the previous 6 months may be used for evaluation of inclusion/exclusion criteria at the judgement of the Principal Investigator:

- ECHO.
- Chest X-Ray.
- PFTs.
- MRI of liver and/or brain and cervical spine.

Further, genetic marker analysis including SNP analysis and MPS I sequencing will not be repeated as results of these assessments do not change over time.

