## 6.3 Baseline

Baseline assessments will be performed within 21 days prior to SB-318 infusion.

In subjects receiving ERT, ERT shall be withheld during the week of the administration of SB-318 to enable accurate baseline testing

The following assessments and procedures will be performed:

- Review and record concomitant medications.
- Physical examination.
- Vital signs.
- Assessment of AEs.
- ERT administration log.
- Joint range of motion (JROM).

- Neurologic cranial nerve exam and muscle strength testing of the upper extremities.
- 12-lead ECG.
- Pregnancy test (for females of childbearing potential only).
- Clinical laboratory tests.
- Liver panel.
- Chimerism assay (for post-HSCT subjects only).
- GAG testing in urine.
- IDUA / GAG testing in blood.
- Vector genome PCR in plasma, saliva, urine, stool, and semen (males only).
- PFTs.
- 6-minute walk test (6MWT).
- Visual acuity test and corneal clouding exam.
- Neurocognitive abilities tests by WASI-II (Wechsler Abbreviated Scale of Intelligence), WPPSI-IV (Wechsler Preschool and Primary Scale of Intelligence), or BSID-III (Bayley Scales of Infant Development), and by VABS-II.
- MRI of brain and cervical spine.
- Adrenocorticotrophic hormone (ACTH) stimulation (cosyntropin) test (prior to prednisone or equivalent corticosteroid).
- Liver biopsy.
- Lumbar puncture.
- Immunogenicity assays.
- Prednisone or equivalent corticosteroid administration (starting 2 days before SB-318 infusion).

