#### **9.19 GAG Testing in Urine and Blood**

GAGs are metabolites that accumulate in MPS I due to lack of active IDUA enzyme. GAG accumulation is responsible for diffuse organ toxicity and damage in MPS I. To monitor the effect of SB-318 administration, GAG levels (including total GAG, DS GAG, and HS GAG) will be measured in urine and tissues (including blood, liver tissue, and CSF) throughout this study. Samples for GAG testing in blood and urine must be obtained 7 days after ERT administration (+/- 1 day) and prior to the next ERT infusion. GAG and IDUA levels in blood will both be measured concurrently from the same blood sample. For details, refer to the Laboratory Manual.

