- e. Liver panel will be performed twice a week for the first 20 weeks post-SB-318 infusion and may be remotely. Blood samples will be drawn 2-4 days apart when possible, except for the first week when it will be drawn on the Day 1 and Day 7 visits. Liver function tests will subsequently be conducted at all indicated study visits.
- f. For adult subjects (cohorts 1 through 3), the assay will be performed on blood or saliva samples. For post-transplant subjects, the assay will be performed on saliva samples only. For pediatric subjects (cohorts 4 through 7), saliva samples are preferred.
- g. For post-HSCT patients only.
- h. During Screening, samples for GAG testing in urine will be collected on 3 separate days, each collection occurring at least 7 days after the previous. All samples for GAG testing in the urine must be collected at least 7 days after ERT administration [+/- 1 day] but prior to the next ERT infusion.
- i. For IDUA/GAG testing in blood, samples must be obtained 7 days after ERT administration (+/- 1 day) and prior to the next ERT infusion. GAG and IDUA levels in blood will both be measured concurrently from the same blood sample.
- j. Each type of sample (plasma, saliva, urine, stool, semen) will be collected until 3 consecutive specimens of that sample type are reported as negative or undetectable for vector genome. Collection of semen samples may be waived for male pediatric subjects (cohorts 4 through 7) at the discretion of Principal Investigator.
- k. As permitted by subject's capacity. Neurocognitive abilities testing in pediatric subjects will be done by VABS-II and by WASI-II, WPPSI-IV, or BSID-III, as appropriate based on the Neurocognitive Abilities Assessment performed at Screening.
- l. Baseline MRI of brain and cervical spine may be obtained at Screening (together with MRI for liver) instead of at Baseline at the discretion of the Principal Investigator.
- m. Should prednisone or equivalent corticosteroid treatment be continued or repeated due to increased transaminase activity, the ACTH stimulation test will be repeated at the end of taper. Vital signs should be monitored and recorded every hour during the ACTH stimulation test.
- n. Unless contraindicated by a Principal Investigator or physician.
- o. May be waived for pediatric subjects (cohorts 4 through 7) at the discretion of the Principal Investigator to minimize required blood volumes.
- p. See [Appendix 3](#).

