8.2.2. Total GAG, DS GAG, and HS GAG

Total GAG, DS GAG, and HS GAG (expressed as a ratio to creatinine) measured in urine will be assessed over time from Screening till Month 36/end of study visit or early termination visit if applicable. Descriptive statistics of the observed values and change from baseline values will be provided at the scheduled visits. A corresponding listing and summary table will be provided.

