SB-318 5.00E+13 vg/kg	XXXXXX	XXX	XXX	XXX

Source Data: Listing 16.2.4.2

<DIRECTORY PATH>PROGRAM NAME Executed: DDMMYYYY hh:mm

Table 14.2.1
Change from Baseline in Plasma and Leukocyte IDUA Activity
Safety Set

Parameter: Alpha Iduronidase Plasma (nmol/hr/mL)

Visit	SB-318 1.00E+13 vg/kg (N=xx)		SB-318 5.00E+13 vg/kg (N=xx)		Total (N=xx)	
	Actual Value	Change From Baseline [1]	Actual Value	Change From Baseline [1]	Actual Value	Change From Baseline [1]
BASELINE						
n	xx		xx		xx	
MEAN (SD)	xx.x (xx.xx)		xx.x (xx.xx)		xx.x (xx.xx)	
MEDIAN	xx.x		xx.x		xx.x	
MIN, MAX	xx, xx		xx, xx		xx, xx	
VISIT X						
n	xx	xx	xx	xx	xx	xx
MEAN (SD)	xx.x (xx.xx)	xx.x (xx.xx)	xx.x (xx.xx)	xx.x (xx.xx)	xx.x (xx.xx)	xx.x (xx.xx)
MEDIAN	xx.x	xx.x	xx.x	xx.x	xx.x	xx.x
MIN, MAX	xx, xx	xx, xx	xx, xx	xx, xx	xx, xx	xx, xx

..
Note: Baseline is defined as last non-missing measurement prior to dosing.

[1]Change from baseline: post-baseline value - baseline value. For the change from baseline, only subjects with a value at both baseline visit and the specific post-baseline visit are included.

Source Data: Listing 16.2.9.3

<DIRECTORY PATH>PROGRAM NAME Executed: DDMMYYYY hh:mm

Prog Notes: Repeat for Alpha Iduronidase Leukocyte (nmol/hr/mL) parameter. Post baseline visits include Day 7, Weeks 2, 4, 6, 8, 12, 16, 20, 24, 36, 48, Months 15, 18, 21, 24, 27, 30, 33, 36/ EOS, or Early Termination Visit if applicable.

Table 14.2.2
Change from Baseline in Urine GAG Levels and Urine GAG/Creatinine Ratio
Safety Set

Parameter: Total Glycosaminoglycans (GAGs) (mg/mmol creatinine)

Visit	SB-318 1.00E+13 vg/kg (N=xx)		SB-318 5.00E+13 vg/kg (N=xx)		Total (N=xx)	
	Actual Value	Change From Baseline [1]	Actual Value	Change From Baseline [1]	Actual Value	Change From Baseline [1]
BASELINE						
n	xx		xx		xx	
MEAN (SD)	xx.x (xx.xx)		xx.x (xx.xx)		xx.x (xx.xx)	
MEDIAN	xx.x		xx.x		xx.x	
MIN, MAX	xx, xx		xx, xx		xx, xx	
VISIT X						
n	xx	xx	xx	xx	xx	xx
MEAN (SD)	xx.x (xx.xx)	xx.x (xx.xx)	xx.x (xx.xx)	xx.x (xx.xx)	xx.x (xx.xx)	xx.x (xx.xx)
MEDIAN	xx.x	xx.x	xx.x	xx.x	xx.x	xx.x
MIN, MAX	xx, xx	xx, xx	xx, xx	xx, xx	xx, xx	xx, xx

...
Note: Baseline is defined as last non-missing measurement prior to dosing.

[1]Change from baseline: post-baseline value - baseline value. For the change from baseline, only subjects with a value at both baseline visit and the specific post-baseline visit are included.

Source Data: Listing 16.2.9.4

<DIRECTORY PATH>PROGRAM NAME Executed: DDMMYYYY hh:mm

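### Change in urine GAG is measured from one pre-infusion sample although four are scheduled; averaging the valid ones would usually reduce noise in cohorts of 1 or 2 subjects

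*SAP*

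**What the plan says.** **Collection.** Protocol section 6.1 asks every subject at Screening to "collect samples on 3 separate days, each collection occurring at least 7 days after the previous". Footnote h of the Schedule of Events (Appendix 1) repeats this: "During Screening, samples for GAG testing in urine will be collected on 3 separate days". Urine GAG is also in the Baseline visit list of section 6.3, where "Baseline assessments will be performed within 21 days prior to SB-318 infusion". That makes four scheduled pre-infusion samples. The blood IDUA/GAG line in section 6.1 asks for no repeat collections. No inclusion or exclusion criterion uses a urine GAG value.

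**Analysis.** SAP section 4 states that "Baseline is defined as the last non-missing measurement prior to the SB-318 infusion" and defines change as the post-baseline value minus that baseline. The footnote of shell Table 14.2.2 (urine GAG) says "Note: Baseline is defined as last non-missing measurement prior to dosing", and the shell has rows only for Baseline and post-baseline visits. SAP 8.2.2 adds only that "Descriptive statistics of the observed values and change from baseline values will be provided at the scheduled visits". Neither 8.2.2 nor the list of changes in SAP section 11 makes an exception for urine GAG.

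When the Baseline-visit sample exists, it alone is the reference. If it is missing, the latest Screening value takes its place. The Screening values are not lost: SAP section 4 puts all collected data in listings, and Listing 16.2.9.4 shows urine GAG by subject, visit and date.

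**The concern.** Change in urine GAG (total, DS and HS, as ratios to creatinine) is a secondary endpoint. The planned cohorts have 1 subject (Cohort 1) or 2, so there is little or no averaging across subjects to absorb a poor baseline value. The baseline error is also shared within a subject: the same number is subtracted at each of the 21 scheduled post-baseline visits in Table 14.2.2 (13 from Week 4 to Week 52, and 8 from Month 15 to Month 36). If that sample happens to be high, every later change looks like a fall; if low, every later change looks like a rise or a failure to fall. Longer follow-up does not remove the error.

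The last-value rule also carries no validity condition. A Baseline sample taken outside the protocol's ERT timing would still be the reference, even with correctly timed Screening samples available.

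**Working it through.** **The plan's own figures.** The documents give no power, precision or SD for urine GAG. The one figure that can be reproduced is maximum enrolment: 1 + 2 × 6 = 13 planned, plus about 2 in each of 7 cohorts, 13 + 14 = 27, as stated. (Protocol 13.1 and SAP 4.1 place the single subject in Cohort 2; the synopsis and cohort tables place it in Cohort 1. The total is the same.)

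**Inputs.** k is the number of pre-infusion samples averaged: 1 under the SAP, 3 for Screening alone, 4 for Screening plus Baseline. s is the within-subject SD of one urine GAG value, which is not in the documents. n is the number of subjects in the cohort.

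**Step 1: one subject, one visit, independent errors.** Var(change) = s²(1 + 1/k).

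| Baseline | Variance | SD | SD reduction |
|---|---|---|---|
| Single last value (k = 1) | 2.00s² | 1.414s | – |
| Mean of 3 Screening values | 1.33s² | 1.155s | 18% |
| Mean of 4 values | 1.25s² | 1.118s | 21% |

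The part shared by all visits has variance s²/k, so its SD falls from 1.00s to s/√4 = 0.50s.

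**Step 2: cohort mean change.** SE = s√((1 + 1/k)/n). Single value against mean of 4: 1.414s against 1.118s at n = 1; 1.000s against 0.791s at n = 2; 0.707s against 0.559s if a cohort of 2 is expanded to 4.

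**Step 3: scale.** With an assumed within-subject CV, the 95% noise half-width as a percentage of baseline is 196 × CV × √((1 + 1/k)/n).

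| Assumed CV | n = 1: single / mean of 4 | n = 2: single / mean of 4 |
|---|---|---|
| 10% | 27.7 / 21.9 | 19.6 / 15.5 |
| 20% | 55.4 / 43.8 | 39.2 / 31.0 |
| 30% | 83.2 / 65.7 | 58.8 / 46.5 |

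**Step 4: serial correlation.** Errors t weeks apart were given correlation ρ^t. Three assumed layouts of pre-infusion days were used (−28, −21, −14, −7; −60, −50, −40, −14; −90, −83, −76, −7), with change taken at Week 4 and Week 24. Ratio of SDs, mean of 4 over single value:

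- ρ = 0: 0.79
- ρ = 0.5: 0.83 to 0.88 (gain about 12-17%)
- ρ = 0.7: 0.86 to 0.94 (gain 6-14%)
- ρ = 0.9: 0.94 to 0.97 at Week 24, but 1.03 to 1.17 at Week 4, where averaging is worse

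**Step 5: varying true response.** If the true response varies between subjects with variance τ², the ratio for the spread of observed changes is √((1.25 + τ²/s²)/(2 + τ²/s²)): 0.87 at τ² = s² and 0.94 at τ² = 4s².

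**Step 6: age of the samples.** Screening may be up to 3 months before Baseline, and Baseline up to 21 days before infusion. Taking 3 months as about 91 days, the oldest sample could be 91 + 21 = 112 days old, nearly 4 months.

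**The case against.** The strongest reply is that this is a design choice and not an error. The last-value rule is explicit and consistently applied, the study is descriptive with no hypothesis tests, and no error rate, power or decision rule depends on it. With 1 or 2 subjects per cohort, the listing in effect gives the individual data, so a reader can see an odd baseline. The protocol's stated provision for accurate baseline urine GAG is the omission of ERT in the infusion week (section 3.5), which fits a late single sample. A recent value is also less exposed to drift. Finally, the shells are dated January 2022 in an open-label study, and SAP 3.2.3 already reports in the past tense that some assays were not done, so a new main baseline could look data-driven.

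Most of this stands as a limit on size. It does not remove the point: where nothing is tested, the descriptive changes are the result, and the samples are already scheduled.

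Some stronger readings are tempting but unsupported:

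- *The Screening values are thrown away.* They are listed, and the latest is the fallback; they are absent only from the change calculation.
- *The three samples exist to set a stable baseline.* No other use is stated, but the documents give no reason for them.
- *Urine GAG is the main pharmacodynamic readout.* The secondary endpoints, which include IDUA activity, are not ranked.
- *All samples follow one ERT-timing rule.* Section 6.1 and footnote h set a minimum of 7 days; section 9.19 says samples "must be obtained 7 days after ERT administration", a fixed interval. Both carry a one-day tolerance and precede the next infusion, but the wordings differ.

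**Conclusion.** The point holds as an avoidable loss of precision in one secondary endpoint. The SAP computes change in urine GAG from one value where the protocol provides up to four. The 21% reduction is for one subject at one visit and assumes independent errors of equal SD and no drift; it should not be read as the expected gain. Moderate serial correlation brings it to roughly 6-17%, and very strong correlation (about 0.9 per week) can make the averaged baseline worse at early visits. The absolute size cannot be stated, because the within-subject CV is not in the documents. No sample size or error rate changes. The case for acting rests on the small cohorts, the baseline error being common to all later visits, and the low cost.

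**What to change.** As an exception to SAP section 4, state in SAP 8.2.2 and the Table 14.2.2 footnote that baseline for total, DS and HS GAG/creatinine is the mean of all valid pre-infusion samples from the current Screening period and the Baseline visit. Limiting it to the current period keeps out samples from an earlier screening, since re-screening is allowed. State which ERT-timing wording, that of section 6.1 and footnote h or that of section 9.19, defines a valid sample; those passages need reconciling first.

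Show the last-value baseline as a sensitivity display, and record the change and its date in SAP section 11, saying whether urine GAG results had been seen. The sensitivity display addresses drift, strong correlation and the late timing.

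The cost is one derived variable, a few sentences, a footnote and one extra display. No new samples are needed, and the pre-dose values are already listed. The small downside is that the averaged baseline can include samples up to nearly 4 months before infusion.
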